1. PURPOSE

The purpose of the study is to compare effectiveness of two repetitive transcranial magnetic stimulation (rTMS) protocols in rehabilitation of aphasia:

1. Inhibitory, low-frequency stimulation of right inferior frontal gyrus,
2. Inhibitory, low-frequency stimulation of right posterior superior temporal gyrus.

2. METHODS

Research Design

Randomized controlled trial

Population

People with aphasia aged between 18-80 whose native language is Turkish

Sample, Inclusion and Exclusion Criteria

20 participants

Inclusion Criteria:

- Right-handedness,
- Normal or corrected-to-normal vision and hearing,
- Aphasia following cerebrovascular accident,
- Cerebrovascular accident at least 6 months prior to enrolment in the study,
- Satisfying current TMS safety guidelines (Rossi et al., 2021, 2009), which are:
 - No previous history of epilepsy,
 - No implants (e.g., cochlear implant) or stimulators (e.g., deep brain stimulation) in the head which may interact with the magnetic field,
 - No use of central nervous system (CNS) active drugs that lower seizure threshold (as listed in the aforementioned guidelines)

Exclusion Criteria:

- Left-handedness, ambidexterity,
- Impaired and uncorrected vision or hearing,
- No aphasia symptoms following cerebrovascular accident,
- Time since cerebrovascular accident less than 6 months,
- Violating current TMS safety guidelines (Rossi et al., 2021, 2009). In other words:
 - Having a previous history of epilepsy,

- Having an implant (e.g., cochlear implant) or a stimulator (e.g., deep brain stimulation) in the head which may interact with the magnetic field,
- Taking central nervous system (CNS) active drugs that lower seizure threshold (as listed in the aforementioned guidelines)

rTMS Interventions

Intervention 1: Right frontal (inferior frontal gyrus) 1 Hz rTMS

Low-frequency (1 Hz) inhibitory rTMS will be administered to right inferior frontal gyrus with the following parameters:

- Frequency: 1 Hz
- Stimulation site: Right IFG (as determined using EEG 10-20 system)
- Intensity: 100% of motor threshold
- Dosage: 20 minutes per day
- Duration: 10 days over 2 weeks (no stimulation during weekends)

Intervention 2: Right temporal (posterior superior temporal gyrus) 1 Hz rTMS

Low-frequency (1 Hz) inhibitory rTMS will be administered to right posterior superior temporal gyrus with the following parameters:

- Frequency: 1 Hz
- Stimulation site: Right posterior superior temporal gyrus (as determined using EEG 10-20 system)
- Intensity: 100% of motor threshold
- Dosage: 20 minutes per day
- Duration: 10 days over 2 weeks (no stimulation during weekends)

Outcome Measurements

1. ADD Scores

Baseline and post-treatment scores obtained from the Turkish Aphasia Language Assessment Test (ADD)

Time Frame: Immediately before and immediately after the intervention

2. Naming Scores

Naming performance (% accurately named pictures & naming latency for correctly named pictures) on the IPNP picture sets

Time Frame: Immediately before, during and immediately after the intervention

3. Eye movements

An eye tracking-while-listening paradigm will be used to determine proportions of dwell time on the correct picture (out of two alternatives) corresponding to auditorily presented Turkish sentences which vary in morphosyntactic complexity.

Time Frame: Immediately before and immediately after the intervention

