3. STATISTICAL ANALYSES

The statistical analyses will be conducted in R (R Core Team, 2013) using the lme4 package (Bates, Mächler, Bolker, & Walker, 2015). Numeric dependent variables (tests scores, naming latency, dwell time) will be analyzed using linear mixed-effects models (LMM), and binary data (accuracy) will be analyzed using generalized linear mixed-effects models (GLMM) with a binomial link function.

The following fixed effects will be entered into the models:

- rTMS interventions (right frontal, right temporal),
- Assessment time (pre, intermediate, post),
- Interaction between rTMS protocol and assessment time.

Participants and items will be included in the models as random effects.

The lmerTest package (Kuznetsova, Brockhoff, & Christensen, 2017) in R will be used to calculate the *p* values (alpha level at .05).

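### Aphasia severity is neither a stated randomisation factor nor a model term, so severity-dependent gain stays in the protocol-by-time test

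*Combined protocol and SAP*

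**What the plan says.** Section 2 (Methods) gives the design as "Randomized controlled trial" and the sample as "20 participants". It names no sequence method, allocation ratio, blocking, stratification or minimisation, and it rules none out. The only language criterion for entry is "Aphasia following cerebrovascular accident", so mild and very severe cases are both eligible. The ADD is scored immediately before and immediately after treatment, so a baseline measure of severity is already planned.

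Section 3 (Statistical Analyses) lists three fixed effects: the two rTMS protocols, assessment time with the pre-treatment visit as its first level, and "Interaction between rTMS protocol and assessment time". It adds that "Participants and items will be included in the models as random effects". No model has a severity term or any other baseline covariate. No sample-size or power calculation is given.

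**The concern.** How much a person with chronic aphasia can gain in two weeks may well depend on how severe the aphasia is. The plan does not say so, and here it is an assumption. If it is true, two things follow.

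- Variation in gain that severity explains stays in the error of the protocol-by-time test and costs power, whether or not the arms happen to balance.
- If chance puts more severe cases in one arm, the contrast in that realised trial is displaced, and the listed fixed effects do not correct it.

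With 20 people, neither effect is negligible. Stratification cannot be introduced once people are allocated, and a covariate chosen after the data are seen would not be pre-specified.

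**Working it through.** The plan states no power, effect size or SD, so there is no figure of its own to reproduce.

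**Inputs.** From the plan: N = 20, two arms, alpha .05, and the fixed effects above. Assumed: two-sided testing, 10:10 allocation, 10 of 20 severe, and a bad split defined as 7:3 or worse. The gap in mean gain between severity halves (g) and the protocol effect (d) are both in units of the within-half SD of change. d = 1.32 is used because it gives about 80% power with 10 per arm when severity is irrelevant. Each participant is reduced to one change score. That is close to the ADD analysis and only a guide for the item-level naming and dwell models.

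**1. Does severity in level matter?** Trials were simulated with a 7:3 split and severity lowering scores by 2 SD at every visit. A mixed model with protocol, time, their interaction and a participant intercept was fitted (150 trials).
- The baseline gap between arms averaged −0.76, against an expected (0.7 − 0.3) × (−2) = −0.80.
- The interaction averaged −0.05, within simulation error of 0.
- Adding a severity main effect left the interaction estimate unchanged.

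So level cancels, and a severity main effect alone would correct nothing in this contrast. In the binomial accuracy model the cancellation holds on the logit scale.

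**2. How often is the split bad?** P(7:3 or worse) = 2 × [C(10,0)² + C(10,1)² + C(10,2)² + C(10,3)²] / C(20,10) = 2 × (1 + 100 + 2025 + 14400) / 184756 = 33052 / 184756 = 17.9%.

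Alternatives:

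| Assumption | Probability |
|---|---|
| 8 severe, arms differ by at least 4 | 17.0% |
| 6 severe, same | 14.1% |
| 4 severe, same | 8.7% |
| 5 severe, same | 3.3% |
| Simple randomisation, 10 severe, severe split 7:3 or worse | 34.4% |
| Simple randomisation, severe proportions differ by at least 0.4 | 12.4% |

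**3. What does a bad split do to the change contrast?** At exactly 7:3 the shift is (0.7 − 0.3) × g = 0.4g. This is 0.20 SD for g = 0.5 and 0.40 SD for g = 1. Type I error (change-score t-test, 18 df) is then 6.3% and 9.5%. Including worse splits, it is about 11% for g = 1 and 16% for g = 1.5.

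For g = 1 it is about 10.9% in the bad 17.9% of allocations and 3.6% in the remainder: 0.179 × 10.9 + 0.821 × 3.6 = 4.9%. The test keeps its level overall.

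**4. Power at d = 1.32.**

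| Allocation and model | g = 0 | g = 1 |
|---|---|---|
| Unstratified, no severity term (as planned) | 80% | 70% |
| Unstratified, severity-by-time term | 77% | 77% |
| Stratified, no severity term | 80% | 71.5% |
| Stratified, severity-by-time term | 79% | 79.5% |

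The adjusted rows do not depend on g, because the term removes it. At g = 0.5 the planned analysis also has about 77%, so without stratification the term roughly breaks even there and gains above it.

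**The case against.** The case against is strong on several points, and most of it stands.

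- A reader might infer that allocation ignores severity. The document does not show that: it describes no method at all, so the gap is an unstated one.
- A reader might infer that nothing in the models deals with severity. In fact the pre-treatment visit, the participant effect and the interaction together remove stable differences in level. Only severity-dependent gain is left, together with the protocol main effect if it were read as a treatment effect.
- A reader might take one bad allocation in six as a property of this trial. It is a result of the assumed severity mix, ratio and cut-off.
- A reader might conclude that the false-positive rate is inflated. Averaged over allocations it is not; the excess is conditional on an unlucky split.
- It is tempting to say that imbalance would push every outcome the same way. Nothing in the plan relates severity to gain on the ADD, accuracy, latency for correctly named pictures or dwell time. Floor and ceiling effects could act in opposite directions.
- Most of the power recovered comes from the covariate (70% to 77%). Stratification adds about 2 points. At a smaller effect the whole package does little: at d = 0.5 power rises only from about 15% to about 18%.

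None of this removes the core: the listed fixed effects leave severity-dependent gain in the error of the key contrast, and the measure needed to address it is already being collected.

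**Conclusion.** The point holds in a limited form. For 20 participants of unrestricted severity, the plan states no randomisation method or stratification factor and omits a severity-by-time adjustment that its own baseline data would support. If severity shifts mean gain by 1 SD, the cost is roughly 10 points of power at d = 1.32 (70% against about 80%). There is also about an 11% type I error in the 17.9% of allocations that split 7:3 or worse. The overall error rate remains 5%.

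These sizes rest on a half-severe sample, fixed 10:10 allocation, a two-level severity factor and one change score per person. The size of g is not in the document. If g is zero, the planned analysis loses nothing. The change is worth making because it is cheap and has to be settled in advance, not because the plan as written is invalid.

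**What to change.** In the SAP, add baseline ADD (preferably continuous and centred) and its interaction with time as fixed effects in the naming accuracy, naming latency and dwell models. For the ADD itself, analyse the post-treatment score adjusted for the baseline score. A severity stratum cut from the pre-treatment ADD would be a coarse copy of that model's own response, and its interaction with time would also pick up regression to the mean.

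In the protocol, state the randomisation method. If allocation has not begun, randomise 1:1 in concealed blocks within two baseline-ADD strata, with the cut-point fixed in advance. Keep the severity-by-time term as well, since stratifying without it recovers little power (71.5%).

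The cost is a short amendment and an allocation list. The ADD must be scored before allocation if it is used to stratify. The change contrast loses one degree of freedom, or two for naming with its intermediate visit. If severity does not predict gain, the loss is under 1 point of power with stratification and about 2 to 3 points without it.

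### Does timing only the pictures named correctly make the naming-latency comparison misleading enough to need a further planned analysis?

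*Combined protocol and SAP*

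**What the plan says.** The Naming Scores outcome in section 2 (Methods, Outcome Measurements) has two parts: the percentage of pictures named accurately, and "naming latency for correctly named pictures". Both are taken "on the IPNP picture sets", at three points: "Immediately before, during and immediately after the intervention". The sample is "20 participants".

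Section 3 (Statistical Analyses) puts latency in a linear mixed model with protocol, time and their interaction. For accuracy, "binary data (accuracy) will be analyzed using generalized linear mixed-effects models (GLMM) with a binomial link function". For both, "Participants and items will be included in the models as random effects". Nothing links the two models. No supporting latency analysis is planned, and the text does not say whether the same pictures return at each assessment.

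**The concern.** A picture contributes a latency only if it was named correctly, and correct naming may respond to treatment. Suppose one protocol brings more pictures within reach and those pictures are the harder, slower ones. That arm's average latency then rises even if nobody names any picture more slowly. The protocol-by-time interaction, which is the treatment comparison, would show slowing in the arm that did better, or would understate a real speed-up. A reader could take a change in the mix of pictures for a change in speed. The accuracy result is not affected.

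**Working it through.** The plan gives no accuracy rate, latency, variance or effect size, so there is no figure of its own to reproduce. From the documents come 20 participants, three naming assessments and the model terms. Everything else below is assumed.

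**Set-up.** Ten per arm, 100 pictures, baseline accuracy 50%.
- logit P(correct) = ability + gain − item − patient-by-picture − trial difficulty. SDs in logits: ability 1, item 1, patient-by-picture 1.0, trial 0.5.
- log latency = person + slope × difficulty − speed effect + patient-by-assessment term + noise. Slope 0.15 per logit; person SD 0.25; noise SD 0.35.

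The shift is roughly slope × (change in mean difficulty of the correctly named pictures in one arm, less that change in the other), counting only difficulty that the participant and item effects do not absorb. It therefore needs unequal accuracy gains and a difficulty–latency link specific to the patient or the trial. Results are log points × 100, about per cent. SD means the SD of the estimate across simulated trials.

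**1. Where the shift should vanish.** With the planned model: equal gains −0.2; no difficulty–latency link 0.0; difficulty shared by all patients 0.4.

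**2. Central case.** One arm gains 1 logit (50% to 66%), the other nothing, and true speed is unchanged.

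| Patient-by-assessment SD | Shift | In SDs |
|---|---|---|
| 0 (stable speed) | 2.4 | 0.75 |
| 0.05 | 2.6 | 0.57 |
| 0.10 | 2.3 | 0.33 |
| 0.15 | 2.3 | 0.22 |

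With an extra gain of 0.5 logit the shift is 1.1–1.3 (0.15–0.39 SD); with 0.25 logit it is 0.7 (0.10–0.21 SD). If naming truly speeds up by 15, the model shows −12.4 to −12.6: attenuated, same sign. If different picture sets are used, the shift is 2.8–2.9 (0.79 SD stable, 0.39 SD at 0.10).

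**3. Wider grid.** There were 54 settings, with gains of 0.5 to 1.5 logits. The shift is below 1 SD in 39 (stable speed), 48 (SD 0.05) and 53 (SD 0.10), that is 72%, 89% and 98%. The maxima are 2.2, 1.7 and 1.2 SD.

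**4. Harsher assumptions, in milliseconds.** Latency SDs were 300 (person), 250 (item), 200 (patient-by-picture) and 350 (trial), with speed stable between assessments. A difficulty–slowness correlation of 0.5 at item, patient-by-picture and trial level, with accuracy gains of 20 points against 0, gives +65 ms; the SD is 28.5, so 65 / 28.5 = 2.3 SD. Dropping the trial-level link gives +21 ms (21 / 29.4 = 0.7 SD). Keeping only the item-level link gives +2 ms, although raw means move by +41 ms. A correlation of −0.3 at all three levels gives −36 ms.

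**5. Would a matched analysis do better?** This keeps pictures that the same patient named correctly at both assessments.
- Central case, stable speed. The planned SD is 2.4 / 0.75 = 3.2, so root-mean-square error is about √(2.4² + 3.2²) = 4.0 (simulated 3.9). Matching cuts the shift to 0.2–0.6 but raises the SD by 18%, to 1.18 × 3.2 = 3.8; its simulated error is 3.7.
- At SD 0.10 the errors are 7.6 planned and 7.8 matched.
- Over the grid, matching has the lower error in 27, 24 and 21 of 54 settings.
- With the inputs of step 4, all three links present and three choices of difficulty weights, the planned shifts are 50, 58 and 63 ms and the matched shifts 36, 44 and 57 ms. Matching removes 14/50 = 28%, 14/58 = 24% and 6/63 = 10%.
- On the log scale, with mainly trial-level difficulty, matching takes 5.0 only to 4.2 and 2.6 only to 1.8.

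**6. Would a reading rule help?** The rule would discount a latency difference that halves or changes sign on matched pictures. When there is no speed effect it flags 29%, 15% and 8% of nominally significant contrasts (SD 0, 0.05, 0.10), so 71%, 85% and 92% pass.

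**The case for a change.** The best case for a change is that this error is systematic. It counts against whichever protocol improves accuracy more, in a trial whose purpose is to compare two protocols. Under the harsher assumptions, the nominal 5% false-positive rate for latency becomes 11% with gains of 10 points against 0, and 53% with 20 against 0. A supporting analysis needs no new data, and writing it down in advance prevents a choice made after the results are seen.

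Part of this stands. Latency is conditioned on a post-randomisation outcome, no check is planned, and the repetition of pictures is left open. The high false-positive rates are correct for their inputs. But those inputs combine a large difference in accuracy gain between two active protocols, a strong link at every level including the single trial, and no drift in a patient's speed between assessments. The documents support none of these, nor even the sign of the link. In that setting the matched analysis also keeps most of the false slowing, because requiring a correct response on both occasions still selects the easy trials. A contrast that survives it would look checked when it had not been. Matching works when the link lies mainly at patient-by-picture level. Without a trial-level link it brings the shift to between −3 and 4 ms, but the planned shift there is only 15–26 ms, under 1 SD.

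**Conclusion.** No change is needed. Restricting latency to correct responses is the natural definition, since a misnamed picture has no time to a correct name. The planned item effect already removes the most obvious distortion. What remains is a conditional shift: 0.22 to 0.75 SD in the central case, usually below 1 SD over the grid, near zero with equal accuracy gains, and above 2 SD only in demanding combinations. All these sizes rest on assumed inputs; only the 20 participants, the assessment times and the model terms come from the plan.

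The available remedy brings no clear gain. It trades bias for variance at about equal total error and does little when trial-level difficulty drives the shift. Whether to show it as description is a matter on which reasonable statisticians differ. The open point about repeated pictures is one that the analysts will settle when they code items. The plan already defines accuracy and latency as one naming outcome, so a careful report will show both, and will not read latency alone as speed if the arms differ in accuracy change.

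### The plan names no by-participant random slope for time; if participants enter as intercepts only, the intervention × time test on sentence-level dwell time can give too many false positives

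*Combined protocol and SAP*

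**What the plan says.** Section 3 (Statistical Analyses) uses linear mixed models for test scores, naming latency and dwell time, and generalized linear mixed models for accuracy. One list serves all of them, introduced by "The following fixed effects will be entered into the models". It contains the intervention, "Assessment time (pre, intermediate, post") and "Interaction between rTMS protocol and assessment time". The random part is one sentence: "Participants and items will be included in the models as random effects". There is no model formula, and nothing says whether participants enter with intercepts only or also with slopes.

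In section 2 (Methods), Outcome Measurements, item 3, the eye-tracking outcome is defined as "proportions of dwell time on the correct picture (out of two alternatives"), for "Turkish sentences which vary in morphosyntactic complexity". It is measured twice: "Time Frame: Immediately before and immediately after the intervention". Complexity appears in no model term, and no separate dwell-time model or analysis by sentence type is given.

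Section 1 (Purpose) states a single aim, to "compare effectiveness of two repetitive transcranial magnetic stimulation (rTMS) protocols in rehabilitation of aphasia".

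**The concern.** Intervention is assigned to people, and the intervention × time term asks whether average change differs between two groups of people. The right yardstick is how much change varies from person to person. A model with participant and item intercepts only has no such component. It treats each sentence as nearly independent information on the arm difference in change, with the trial-level residual as error and many hundreds of degrees of freedom.

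If some participants improve more than others for reasons unrelated to the stimulation site, that model can report the chance imbalance between the arms as a significant site difference. The problem grows with the number of sentences, because more sentences shrink the trial-level error but not the variation between people. The p value for the site comparison would then be unreliable.

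A smaller matter is that complexity is a planned feature of the stimuli with no planned analysis. The model returns a site difference averaged over sentence types and cannot show whether that difference depends on type. An analysis by complexity added later would be post hoc.

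**Working it through.** **Inputs from the documents.** 20 participants (section 2); alpha .05 (section 3); two eye-tracking times (section 2). The sample size is given without power, effect size or SD, so there is no plan figure to reproduce.

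**Assumed, because the documents do not give them.** 10 per arm; two-sided test; sentence-level data; J = 20, 40 or 80 sentences in total, the same for both arms; trial SD σ = .25; SD of true change between participants τ = 0, .04, .08 or .12.

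**Step 1: true variance.** A participant's mean change has variance τ² + 2σ²/J. The arm difference in mean change therefore has variance (2/10)(τ² + 2σ²/J).

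**Step 2: variance used by an intercepts-only model.** It is approximately (2/10)(2σ²/J), with residual degrees of freedom of 40J − (J + 21), which is 1539 at J = 40. The participant-level comparison has 18.

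**Step 3: ratio and false-positive rate.** The ratio of true to assumed variance is 1 + Jτ²/(2σ²). The approximate error rate is 2[1 − Φ(1.96/√ratio)].

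Example with J = 40 and τ = .08: 2σ²/J = .125/40 = .003125 and τ² = .0064. The ratio is .009525/.003125 = 3.048, with square root 1.746. Then 1.96/1.746 = 1.123, which gives 26.2%.

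**Step 4: simulation.** Balanced null data were analysed with participant and item intercepts only (balanced-ANOVA equivalent, 4000 runs per setting). The rates sit slightly below the formula, mainly because some of the variation in change leaks into the residual.

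| Change SD τ | Formula, J = 20 / 40 / 80 | Simulation, intercepts only | Simulation, participant-level error |
|---|---|---|---|
| 0 | 5.0 / 5.0 / 5.0% | about 5% | about 5% |
| .04 | 8.0 / 11.1 / 16.8% | about 7–8 / 10–11 / 16% | about 5% |
| .08 | 16.8 / 26.2 / 38.5% | about 16 / 25 / 37% | about 5% |
| .12 | 28.1 / 40.8 / 54.0% | about 26 / 40 / 53% | about 5% |

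**Step 5: what the correction does to precision.** At J = 40 and τ = .08, the intercepts-only standard error is √(.2 × .003125) = .025, for a half-width of 1.96 × .025 = .049. The participant-level standard error is √(.2 × .009525) = .0436, for a half-width of 2.101 × .0436 = .092.

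**Step 6: complexity.** Omitting a complexity main effect as large as one trial SD left the averaged estimate at about zero under the null. Its error rate was 4.1% (intercepts only, no variation in change) and 5.4% (participant-level error, τ/σ = .3). The omission does not bias the averaged test.

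Now assume two levels of k = 20 sentences each and τ = .08. The three-way contrast has half-width 2.101 × √(.2 × .25/20) = .105. It is 2.101 × √(.2 × (.0064 + .25/20)) = .129 if participants also vary in time × complexity change with SD .08.

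Suppose a raw site difference of .149 is confined to the complex half. The average is then .0745, and power (noncentral t, 18 df) for the averaged test is 37%. Holding .149 fixed, averaged power is 29%, 37% and 42% at k = 10, 20 and 40. Three-way power is 51%, 80% and 98% if participants do not vary in time × complexity change, and lower if they do.

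**The case against.** The strongest reply is that the plan does not specify intercepts only. It is silent, and an analyst might fit slopes. That is fair, and a reader should not infer that the plan commits to a wrong model. But with no slope named, intercepts are the literal reading, and two analysts following the text could report different p values.

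It would also be too strong to say that the test is reliable only with random slopes. Intercepts alone hold 5% if true change does not vary between participants, or if dwell time is reduced to one value per participant per time. The second case fits poorly with an item random effect, which points to sentence-level data. The first is an assumption that the plan gives no ground for.

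On complexity, most of the objection stands. A reader might infer that leaving it out biases the dwell-time result or leaves an aim unmet. Neither follows. The stated purpose is to compare the two protocols and names no hypothesis by sentence type. The average over the same or balanced sentences answers it without bias, and item intercepts absorb stable differences between sentences. A reader might also suppose that the sites could have opposite effects that cancel. That needs opposite effects with equal weights, and nothing in the documents suggests it. Adding a complexity interaction would not restore power to the averaged test either.

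**Conclusion.** The concern holds as a gap in the specification, minor in severity and cheap to close. If participants enter as intercepts only, the intervention × time test on sentence-level dwell time is anti-conservative whenever true change varies between participants. Under the assumed values the error rate is 16–37% at a change SD of .08 and 7–16% at .04, against a nominal 5%. The direction follows from the model structure. The size rests on an assumed trial SD, change SD, sentence count and equal arms, none of which the documents give. The random-effects sentence covers all models, so the same question arises for naming latency and naming accuracy, although the figures here are for dwell time only.

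The missing complexity term is a secondary, optional point. It limits what the model can show about sentence types. It does not invalidate the averaged comparison.

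**What to change.** 1. State in section 3 that every item-level model (dwell time, naming latency, naming accuracy) includes a by-participant random slope for time as well as the participant and item intercepts. Where the data are one value per participant per time, such as a total test score, the slope is not needed and cannot be separated from the residual.
2. State the fallback for dwell time: if the fit is singular or does not converge, compare participant-mean pre–post changes between the arms (18 df with 20 participants). Naming has a third assessment and so a larger random part; its fallback should be written down as well.
3. Optional: either say that only the average over sentences is of interest, or add centred complexity with intervention × time × complexity as one supportive secondary test. Include by-participant slopes for the terms tested, and keep the averaged contrast as the deciding one.

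**Cost.** SAP wording only; no new data. Confidence intervals widen, for example from ±.049 to ±.092 in the 40-sentence setting above, but the wider ones are honest. The optional test would be imprecise with 20 participants (about ±.105 to ±.129 in that setting). A null result would not show that the sites act alike across sentence types, and the averaged test would stay diluted if the effect is confined to some sentences.
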